8.2. Overview of Other Efficacy Endpoints

Table 13 provides an overview of the planned analyses of other efficacy endpoints, with further details of data displays being presented in Appendix 12: List of Data Displays.

Table 13 Overview of Planned Other Efficacy Analyses

Endpoint	Sum	Summary					
	T	F	L				
Disease Activity							
SELENA SLEDAI Change from BL	Υ [1]	Υ					
SELENA SLEDAI % Change from BL	Υ [1]	Y					
SLICC/ACR Damage Index Observed and Change from BL	Υ [1] [2]		Υ				
SLICC/ACR Damage Index Worsening	Y [2]						
PGA % Change from BL	Υ [1]	Y					
Flares							
Time to First SFI Flare	Υ	Υ					
Number of Severe SFI Flares (and rate per 100 PY)	Υ						
Number of SFI Flares (and rate per 100 PY)	Υ						
Time to First 1A/2B BILAG Flare	Υ	Y					
Time to First BILAG A Flare	Υ	Y					
Organ-Specific Measures							
Time to First Renal Flare	Υ	Υ					
Proteinuria % Change from BL (among subjects with BL proteinuria)	Υ [1]	Y					
Proteinuria Shifts from BL	Υ						
Prednisone							
Prednisone % Change from BL	Υ [1]	Υ					
Prednisone Dose Reduced to \leq 7.5 mg/day (among subjects with BL dose > 7.5 mg/day)	Υ	Υ					

NOTES:

- BL = Baseline, T = Table, F = Figure, L = Listing, Y = Yes display generated, (xN) = Number of separate displays generated
- Summary = Represents TFL related to any summaries (i.e. descriptive statistics) of the observed raw data.
- Individual = Represents FL related to any displays of individual subject observed raw data.
- [1] A combined display will be generated for Absolute and Change from baseline for each laboratory parameter.
- [2] Data summarised separately by parent study. See Section 5.1.

8.2.1. SELENA SLEDAI Change from Baseline

The absolute values, the change, and the percent change from baseline in SELENA SLEDAI scores will be summarised using descriptive statistics, and presented by parent randomised treatment group and the total Safety population, for each belimumab visit

(every Week 24 and Week 48 visit). In summaries, decreases will reflect improvement in the assessment.

Data will be displayed graphically over time using a line graph for the total Safety population. Separate plots will be produced for the mean change from baseline (± SE) and mean percent change from baseline in SELENA SLEDAI score.

8.2.2. SLICC/ACR Damage Index

- The absolute values and change from baseline in SLICC/ACR Damage Index will be summarised using descriptive statistics, and presented by the parent randomised treatment group, for each belimumab visit. This data will be presented separately for subjects from each parent study.
- The SLICC/ACR Damage Index increases over time, and once an item is scored it
 continues to be scored at all subsequent assessments, even if the subject subsequently
 recovers.
 - Oue to incorrect scoring, the database contains a small number of subjects who have at least one decrease in SLICC/ACR Damage Index since baseline.
 - Where the error occurred at closed sites, data management were unable to query and correct the error.
 - Due to these incorrect assessments, a worst score observation carried forward (WOCF) approach will be used at the item level for the SLICC/ACR Damage Index items. These WOCF values will then be used to calculate the total score which will be the value summarized and displayed for reporting.
- The number and percentage of subjects with a worsening in their SLICC/ACR Damage Index score compared with baseline (change score > 0) will be summarized.

See Appendix 5: Derived and Transformed Data for the derivation of SLICC/ACR Damage Index score including Worst Observation Carried Forward (WOCF).

8.2.3. Physician's Global Assessment Change from Baseline

The absolute values and percent change from baseline in PGA will be summarised using descriptive statistics, and presented by the parent randomised treatment group and total Safety population, for each belimumab visit (every Week 24 and Week 48 visit). Total Safety population data will be displayed graphically using a line graph. The plot will show the mean change from baseline (\pm SE) over time.

See Appendix 5: Derived and Transformed Data for the derivation.

8.2.4. Time to First SFI Flare

A SFI flare is defined as a mild/moderate or severe flare per the modified SELENA SLEDAI SLE Flare Index. Analyses of the first SFI flare will use the same methodology as for severe SFI flares (see Section 8.1.6).

8.2.5. Number of SFI Flares and Rates

The number of SFI flares (each for severe flares and any flares) will be summarised at any time post-baseline, and presented by the parent randomised treatment group and the total Safety population. Rates of flares per 100 person-years will also be reported.

The table will display the total number of SFI flares (each for severe flares and any flares), total person-years of follow-up for SFI flare assessments, and the rate of flare events per 100 person-years. See Section 11.5.4.5 for the derivation of the SFI flare rate.

8.2.6. Time to First 1A/2B BILAG Flare

A 1A/2B BILAG flare is defined as at least 1 new BILAG A or 2 or more new BILAG B organ domain scores compared to baseline. Note, a BILAG assessment needs to be performed to determine if there is a change in organ domains. Every 6 month BILAG assessments in BEL114333 will not allow the same reporting as in the parent study (every 4 weeks).

Time to first 1A/2B BILAG flare is calculated as the number of days from first dose of belimumab treatment up to the first BILAG flare event (event date – first belimumab dose date + 1). The event date is defined by the BILAG assessment date. The disposition of subjects is defined as follows:

Subject Disposition	Event Met	Event Date
Subject has a 1A/2B BILAG flare		
Subject has a BILAG flare during the study	Yes	Date of first BILAG flare
Subject does not have a 1A/2B BILAG flare		
Subject withdraws from the study	No	Censored at last available BILAG assessment
Subject dies during the study	No	Censored at date of death.
Subject completes the study *	No	Censored at last available BILAG assessment

^{*}As per the protocol. Includes subjects who transferred to study BEL116027, or who were still participating in the study at the time of the sponsor decision to close/terminate the study

Analyses for the first 1A/2B BILAG flare will use the same methodology as for severe SFI flares (see Section 8.1.6).

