6.2.3. BILAG

The BILAG index is a clinical measure of lupus disease activity. The scoring system for the BILAG index was developed based upon the principle of the physician's intention to treat. The main distinguishing feature of the BILAG index from other disease activity indices is that disease activity in different organs/systems is reported separately. There are 8 organ systems: general, mucocutaneous, neurological, musculoskeletal, cardiorespiratory, vasculitis, renal, and hematological [[Hay, 1993](#); [Isenberg, 2000](#); [Gordon, 2003](#)]. A score is calculated for each system depending on the SLE clinical manifestations (or signs and symptoms) present and whether they are new, worse, the same, improving, or not present in the last 4 weeks compared with the previous 4 weeks. The SLE disease manifestations considered severe in each system are those that would normally require high dose steroids (prednisolone > 20 mg/day or equivalent) and/or cytotoxic agents; these define a BILAG A score. More moderate SLE disease manifestations that would be considered appropriate to treat with lower dose steroids, antimalarial drugs or NSAIDs contribute to a BILAG B score. Mild symptomatic SLE features that require only symptomatic therapy (e.g., analgesics and NSAIDs) contribute to a C score. If there are no current symptoms, but the system has previously been involved, then a D is recorded, while if the system has never been involved an E score is assigned.

The BILAG will be assessed at Day 0 and then every 24 weeks thereafter.

A copy of the BILAG index is provided in [Appendix 2](#). All site staff scoring BILAG assessments are required to pass proficiency tests before carrying out assessments to ensure consistency across centres.

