2.4.1. Treatment Comparisons

All subjects will be treated with open-label IV belimumab for the duration of the study BEL114333. The analyses will be performed on data from all subjects as one total belimumab treatment group by year of belimumab treatment.

As subjects started to receive belimumab treatment in the parent study, or the open-label extension of the parent study BEL112341, or the open-label study BEL114333, different time points to start of belimumab treatment will be used to define subject follow up in the analysis. See Figure 1.

Analyses will be based on all available follow-up from the first dose of belimumab treatment through to study end.

Additional safety (e.g., labs), efficacy and study population summaries will be presented by parent study randomised treatment groups (belimumab vs placebo); however, these comparisons will be descriptive in nature. For the remainder of the document, parent randomised treatment group will be used to refer to the treatment to which a subject was randomised in the parent study, irrespective of formulation.

Figure 1 First Belimumab Dose/Baseline Definition

Analyses will be based on all available data from the first belimumab dose through to study end, BEL114333. As subjects started to receive belimumab in the parent study, or the open-label extension of BEL112341, or the open-label study BEL114333, different timepoints to start of belimumab treatment are used in the analysis (as shown). Baseline is defined as the last available value prior to the first belimumab dose.

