• A complete BEL113750 database extraction will be performed (because the DB data will be used in the open-label analyses). Note, there are differences between the prior DB data extraction by a different vendor/format and the open-label data. The complete extraction will enable all the data to be compatible.

The complete extraction will be able to include any additional parent study information (e.g., SAEs, concomitant meds) entered by sites at any time from the start of the parent study, and will be included in aggregate reporting.
 Note any additional SAEs will also be mentioned separately in the open-label phase CSR.

The same database captures data for BEL114333. Similarly, the BEL114333 sites had the ability to also change data pertaining to the parent study BEL113750, per the above

- From the complete database, a selected data extraction of the BEL114333 data will be performed
- The DB data for Japan and Korea subjects will be extracted from the complete BEL113750 data (previously used for the BEL113750 China OL analysis).

Lastly, the BEL112341 Japan subjects who entered BEL114333 will have all relevant data extracted from the complete BEL112341 database.

All relevant belimumab data from the parent studies and study BEL114333 will be aggregated.

Unless otherwise stated, the following statistics will be used to summarise the data:

- Continuous Variables: n, mean, standard deviation (SD), median, 25th & 75th percentiles, minimum and maximum.
- Categorical Variables: n, frequency counts and percentages.

Unless otherwise stated, the following rules will be implemented:

- Summaries by Visit: Only scheduled visits will be presented (i.e. that correspond to the timings of the open-label visits for BEL114333). Otherwise data not shown here will be displayed in listings, and used in derivations such as "any time post-baseline" summaries for laboratory data, time to event, etc. Exit visits will be slotted to the next 6 monthly scheduled visit for that year for efficacy endpoints (or next 12 monthly scheduled visit for SLICC). Otherwise, data will be summarised per the nominal visit.

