8.2.8. Time to First Renal Flare

Only time to first renal flare will be analysed. Although a renal flare rate was of interest at the time of the protocol design writing, renal flare rates have been relatively

uncommon, and do not provide much clinical value at this current time. Focus will be placed upon providing a summary of the first renal flare event.

Assessments every 6 months during BEL114333 will not allow the use of the same definition of renal flares as in the parent studies, which requires assessments to be performed at two or more consecutive monthly visits. Thus, a renal flare is defined as the occurrence of one or more of the following criteria at a single (belimumab) visit at every Week 24 and Week 48, timepoints at which both protein creatinine ratio and lab assessments are scheduled in the protocol. Note, when identifying renal flares, data within the visit window at Week 24 and Week 48 visits will be considered.

- 1. An increase in 24-hour urine protein equivalent levels to
 - a. > 1 g if the baseline value was < 0.2 g,
 - b. > 2 g if the baseline value was 0.2 to 1 g, or
 - c. More than twice the value at the baseline if the baseline value is > 1 g.
- 2. An increase in serum creatinine of >20 % or an increase of at least 0.3 mg/dL, accompanied by at least one of proteinuria (>1 g/24 hour equivalent), hematuria (≥ 4 red blood cells [RBCs]/high-power field [hpf]), cellular (RBC or WBC) casts. The inclusion of 'at least one of' and 'RBC or WBC' casts is an addition to the protocol specified definition. This addition has been included in the parent study BEL113750 RAP.
- 3. Treatment-emergent, hematuria (≥ 11 to 20 RBCs/hpf) or an increase in hematuria by 2 grade compared with baseline, associated with > 25% dysmorphic RBCs, glomerular in origin, exclusive of menses, accompanied by either an 0.8 g increase in 24-hour urinary protein levels (equivalent) or new RBC casts [Alarcón-Segovia, 2003].

To clarify criterion 2, [an increase in serum creatinine of > 20% OR an increase of at least 0.3 mg/dL], AND [proteinuria (> 1 g/24-hour equivalent) OR hematuria (≥ 4 red blood cells {RBCs}/high-power field {hpf}) OR cellular (RBC or WBC) casts].

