11.1.2.2.2. BEL112341 - Open-Label Phase

	Day 0 A (± 1 day)	Day 28 Visit ±7 day	Day 84 Visit ± 7 day	Day 168 Visit ±7 days	Exit visit for non-completers ^B	8-wk Follow- up Visit ^H (8 wks post last dose) ± 7 days
OO administration of halfmanniah	VR	Wk 4	Wk 12	Wk 24 ekly (+/- 1 day) v	with final doco	at Wook 23
SC administration of belimumab	XB		vve	ekiy (+/- i day) v	VIIII IIIIai uose i	at week 23
Clinical Assessments: Adverse Events		X	Х	Х	X	X
Collect self-injection logs; record dosing in CRF		X	X	X	X	^
Record All Concurrent Medications		X	X	X	X	X
Weight		^	^	X	X	^
Symptom-driven PE				X	X	
SLE Disease Activity Scales ^C	— p			X	X	
SLICC/ACR Damage Index	erio			X	X	
FACIT-Fatigue Scale ^D	ri it			X	X	
Laboratory Assessments:	4/E)					
Urine Pregnancy Test ^E	/ 36,	Х	Х	Х	Х	X
Urinalysis	Mk 1			Х	Х	X
Spot Urine Protein Creatinine Ratio	See Day 364/Exit Visit in 52-Wk Treatment Period			Х	Х	
PT/PTT	.E			Х		
Hematology & Modified Chem 20 (non fasting) F				Х	Х	X
Complement (C3/C4) and anti-dsDNA				Х	Χ	
Serum Immunoglobulin (IgA, IgM, IgG)			Х	Х	Χ	
B-Cells				Х	Χ	
Immunogenicity ^G				Х		X
See Footnotes on next page						

L Pharmacogenetic sampling informed consent must be obtained prior to any blood being taken for PGx research. Sample should be drawn prior to dosing, or the sample may be taken at any time while the subject is participating in the clinical study

MC-SSRS Since Last Visit (see Protocol, Appendix 12) will be used at Day 0 and all subsequent visits. The C-SSRS Baseline/Screening form (see Protocol, Appendix 11) is only used at Screening.

- A Day 0 of the extension portion of the trial is the Week 52 study visit of the double-blind phase, and represents the first belimumab administration in the open-label phase for those subjects continuing on the 6-month open-label study (see Protocol, Table 6.1). The visit schedule is based on the schedule for the 52-week double-blind phase. The visit window is ± 1 day.
- B The exit visit is scheduled for Week 24, one week after the last dose of study agent. Subjects who discontinue study agent before Week 23 must complete an exit visit 1-4 weeks after the last dose of study agent
- ^C SLE Disease Activity Scales: SELENA SLEDAI, SLE Flare Index, BILAG, PGA.
- ^D Must be completed by the subject prior to any study-related discussion with the investigator or study coordinator. The FACIT-Fatigue Scale will only be completed by subjects for whom a survey exists in the subject's language.

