11.6.2.2. Handling of Missing Data for Statistical Analysis

Element	Reporting Detail
General	 The efficacy endpoints will be summarised using observed case data, for all subjects in the Safety population, unless otherwise stated. Assessments not done will remain as missing.
SLICC/ACR Damage Index	 The Index is cumulative, once an item is scored it should continue to be scored for all subsequent assessments (see Section 11.5.4.4). Where an assessment is completed (at least one item was marked or a total score of 0 was recorded), items left unchecked on the SLICC/ACR, and not previously checked, will be considered as "not present" (rather than missing), and assigned an item score of 0 in the analysis dataset (see Section 11.5.4.4).
SELENA SLEDAI	Where an assessment is completed (at least one item was marked or a total score of 0 was recorded), items left unmarked on the SELENA SLEDAI will be considered as "not present" (rather than missing), and assigned an item score of 0 in the analysis dataset (see Section 11.5.4.1).
BILAG	As OL BILAG assessments are every 6 months vs monthly for the DB part of the parent studies, items left unmarked on the questionnaire will not be imputed. See Section 11.5.4.2, for the derivation of organ domain scores with missing data.

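### Time to first BILAG flare mixes 4-weekly and roughly 24-weekly assessments, so Year 1 incidence by parent group and the curve around Week 52 partly reflect how often BILAG was scored

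*SAP*

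**What the plan says.** **Assessment schedules.** For BEL114333, Protocol 6.2.3 states: "The BILAG will be assessed at Day 0 and then every 24 weeks thereafter". SAP 11.6.2.2 acknowledges the contrast with the parent studies: "As OL BILAG assessments are every 6 months vs monthly for the DB part of the parent studies". The parent schedules in SAP 11.1.2 show BILAG at Weeks 4 to 48 every 4 weeks and again at Week 52, in both double-blind phases. In the BEL112341 open-label extension (SAP 11.1.2.2.2), the row footnoted "SLE Disease Activity Scales: SELENA SLEDAI, SLE Flare Index, BILAG, PGA" is completed after Day 0 only at Day 168 or on early exit.

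**Derivation.** SAP 2.4.1 sets the time origin: "Analyses will be based on all available data from the first belimumab dose through to study end, BEL114333". SAP 8.2.6 notes the difference in spacing: "Every 6 month BILAG assessments in BEL114333 will not allow the same reporting as in the parent study (every 4 weeks". In SAP 8.2.6, "The event date is defined by the BILAG assessment date", with no limit on which visits qualify. SAP 8.2.7 applies the same approach to BILAG A flare. SAP 5.1 restricts by-visit summaries to BEL114333 visit timings, but sends the remaining data to listings and to derivations, including "summaries for laboratory data, time to event, etc".

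**Display.** The method is borrowed from SAP 8.1.6: Kaplan-Meier summaries by parent randomised group and in total, and one cumulative incidence curve for the total Safety population.

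**Renal flare.** SAP 8.2.8 does name its visits: "when identifying renal flares, data within the visit window at Week 24 and Week 48 visits will be considered".

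**The concern.** A flare that starts and settles between two visits 24 weeks apart can be missed. The same flare under 4-weekly scoring is very likely to be recorded. Only subjects randomised to belimumab bring 4-weekly scores into the analysis, because the placebo subjects' monthly scores precede their first belimumab dose. This has two consequences:

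- The two parent groups are compared over their first belimumab year on different schedules.
- Within the belimumab-origin group, the schedule changes at about Week 52, so recorded flares can thin out there although the disease has not changed.

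The SAP's Table 1 justifies total-population graphs by their use in reading response over time, and a change of schedule partway along the curve interferes with that reading. The SFI method borrowed for BILAG had a between-visit flare log in BEL114333 (SAP 8.1.6). No such log is described for BILAG.

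**Working it through.** The plan states no flare rate, event count or sample size for this endpoint, so there is no figure to reproduce.

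**Assessments in belimumab Year 1 (SAP 11.1.2 and 11.2.2)**
- Randomised to belimumab: Weeks 4, 8, …, 48 (12) plus Week 52 = 13.
- Randomised to placebo, from BEL113750: BEL114333 Weeks 24 and 48 = 2.
- Randomised to placebo, from BEL112341: extension Day 168 and BEL114333 Week 24 = 2.

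**Assumptions (not from the documents).** Flares start at a constant rate λ per year, the same in both groups. Duration is exponential with mean D weeks. The one documented input is the 4-week look-back in Protocol 6.2.3: a flare is scored if it is active at the visit or ended within the previous 4 weeks.

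**Formula.** For a gap of g weeks between visits, the number of onset weeks that lead to detection is w(g) = 4 + D(1 − exp(−(g − 4)/D)), and w(g) = g if flares are permanent. With g = 4 every onset is caught. Cumulative incidence is 1 − exp(−λ·Σw/52).

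**Share of onsets caught at 24-week spacing, w(24)/24.** This does not depend on λ.
- D = 4: 7.97/24 = 33%
- D = 8: 11.34/24 = 47%
- D = 16: 15.42/24 = 64%
- Permanent: 24/24 = 100%

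These shares are also the factor by which the recorded flare rate in the belimumab-origin group would change after about Week 52 at a constant true rate.

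**Year 1 incidence at λ = 0.5**

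| Mean duration | 4-weekly, to Week 52 | 24-weekly, Weeks 24 and 48 | Belimumab-origin on common grid, Weeks 24 and 52 |
|---|---|---|---|
| 4 weeks | 39.3% | 14.2% | 14.2% |
| 8 weeks | 39.3% | 19.6% | 19.8% |
| 16 weeks | 39.3% | 25.7% | 26.4% |
| Permanent | 39.3% | 37.0% | 39.3% |

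Example, D = 8:
- 24-weekly: 2 × 11.34 = 22.69 weeks, and 1 − exp(−0.5 × 22.69/52) = 19.6%.
- Common grid: w(24) + w(28) = 11.34 + 11.60 = 22.94 weeks, giving 19.8%.

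A simulation of 100,000 subjects per scenario agrees with this table to within about 0.3 of a point.

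Part of the raw gap is only the 4 extra weeks. At Week 48 the 4-weekly figure is 1 − exp(−0.5 × 48/52) = 37.0%, which equals the 24-weekly figure for permanent flares.

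**Range over λ, with D = 8 (simulation).** At 0.2 per year, 18.2% against 8.4%. At 1.0 per year, 63.2% against 35.3%.

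**Timing.** Up to Week 20 the 24-weekly group has had no scheduled assessment and shows 0%. The 4-weekly group shows 1 − exp(−0.5 × 20/52) = 17.5%, whatever the duration.

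**The case against.** **Which visits count is inferred.** SAP 8.2.6 does not say that every assessment is eligible, and the worked BILAG example in SAP 11.5.4.2 shows only Week 24 and Week 48 rows, Year 1 included. This has some force, since the surrounding BILAG text is redacted and the rule in 5.1 applies only unless stated otherwise. But the example is an illustration, whereas 5.1 mentions time-to-event derivations expressly. If the Week 24/48 grid was intended, 8.2.6 needs to say so.

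**Renal flare is not an inconsistency.** A reader might infer that the SAP treats two like endpoints differently without reason. The documents do not support this. SAP 8.2.8 and Table 1 explain that the parent definition needed two consecutive monthly visits, which BEL114333 could not supply, and that Weeks 24 and 48 are where the urine ratio and laboratory tests coincide. BILAG flare has no such rule. SAP 8.2.8 shows only that the grid is workable.

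**Flares between visits are not always lost.** The 4-week look-back can capture one that has just settled. Flares are also judged against a fixed baseline, so lasting activity is still found at the next visit.

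**The endpoint is low in the hierarchy.** It is an other efficacy endpoint in a descriptive, safety-primary study, with no test or hazard ratio, and 8.2.6 discloses the spacing. That limits the consequence to interpretation. Disclosing the spacing does not make the tables comparable.

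**Conclusion.** The point holds as a matter of interpretation. As written, the plan gives 13 assessments against 2 in belimumab Year 1. Incidence by parent group and the shape of the pooled curve near Week 52 therefore partly reflect assessment frequency. The effect is substantial if flares are transient and small if they persist: in the scenarios above, the Year 1 gap at 0.5 flares per year runs from about 25 points (4-week flares) to about 2 points (permanent flares). These sizes rest wholly on assumed rates and durations.

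Two stronger readings are tempting. One is that the curve simply measures visit frequency; the permanent-flare case shows that this need not be so. The other is that a parent-group gap would look like a belimumab-versus-placebo effect. Both groups receive belimumab from time zero, and SAP 2.4 calls any comparison between them descriptive, so error rates are not at issue.

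**What to change.** In SAP 8.2.6 and 8.2.7, derive BILAG flare events and censoring on the common Week 24/Week 48 belimumab-visit grid for Tables 3.19 to 3.22 and Figures 3.10 and 3.11. The text should state:

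- Parent Week 52 counts as Year 1 Week 48 for subjects randomised to belimumab, as mapped in 11.2.2.
- Exit visits are slotted to the next 6-monthly visit, as in 5.1.
- Subjects without a flare are censored at their last assessment on this grid.

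Keep the all-assessments version as supportive, with a footnote giving the assessment frequency by parent group and period.

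The change costs a few sentences and one filter, and needs no new data. The downside is that the main display omits flares seen only at interim parent-study visits and so has fewer events. A 4-week timing difference (Week 52 against Week 48) also remains. In the scenarios above at 0.5 flares per year it is worth less than 1 point for transient flares and about 2 points for permanent ones (39.3% against 37.0%). At 1.0 per year the permanent-flare difference is about 3 points: 1 − exp(−52/52) = 63.2% against 1 − exp(−48/52) = 60.3%.
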